6.3. Lifestyle Restrictions

There are no specific lifestyle restrictions for this protocol.

6.4. Screen Failures

Individuals who do not meet the criteria for participation in this study (screen failure) may be rescreened. Individuals may be rescreened a maximum of 2 times. The interval between rescreenings should be ≥ 2 weeks. Each time rescreening is performed, the individual must sign a new informed consent form (ICF) and will be assigned a new identification number. Repeating of laboratory tests during the screening period or repeating screening tests to comply with the protocol-designated screening period does not constitute rescreening.

7. Treatments

7.1. Treatments Administered

Patients in all cohorts will receive 105 mg/m² prexasertib as an approximately 60 (+10) minute intravenous (IV) infusion on Day 1 and 15 of a 28-day cycle.

The investigator or his/her designee is responsible for the following:

- explaining the correct use of the drug and planned duration of each individual's treatment to the patient/study site personnel/legal representative
- verifying that instructions are followed properly
- maintaining accurate records of prexasertib dispensing and collection
- at the end of the study returning all unused medication to Lilly, or its designee, unless Lilly and sites have agreed all unused medication is to be destroyed by the site, as allowed by local law.

7.1.1. Packaging and Labelling

The drug product, prexasertib (LY2606368) for injection, is supplied for clinical trial use as a lyophilized, yellow to white powder, in glass vials and is composed of prexasertib lactate monohydrate and the inactive ingredients trehalose, polysorbate 80 and mannitol. Clinical trial materials will be labeled according to the country's regulatory requirements.

7.2. Method of Treatment Assignment

Upon obtaining informed consent, the site will register the patient via the interactive web response system (IWRS), which is accessible 24 hours a day, to assign a patient number. Patients who meet all criteria for enrollment will be assigned to a cohort based on *BRCA* status, platinum resistant vs refractory, and/or lines of prior therapy. The IWRS will be used to dispense study drug to and/or track the allocation of each patient.

7.2.1. Selection and Timing of Doses

A cycle is defined as an interval of 28 days.

The actual doses of study treatment to be administered will be determined by calculating the patient's BSA at the beginning of each cycle. Although it is acceptable to recalculate more frequently, if the patient's weight does not fluctuate by more than $\pm 10\%$ from the weight used to calculate the prior cycle or from baseline, the BSA will not need to be recalculated. A $\pm 10\%$ variance in the calculated total dose will be allowed for ease of dose administration.

A patient may continue to receive study treatment until she meets 1 or more of the specified reasons for discontinuation.

7.3. Blinding

This is an open-label study.

7.4. Dose Modification

The following rules should guide dosing:

- Before each dose:
 - Nonhematologic toxicities must resolve to Grade 0 or 1 or baseline, except AEs with no immediate medical consequence or those that can be controlled with adequate treatment (for example, pain, alopecia, fatigue, nausea, vomiting, or diarrhea)
 - Neutropenia and anemia must resolve to Grade ≤ 2 , and thrombocytopenia to Grade ≤ 1 , as shown in [Table JTJN.6](#).

Table JTJN.6. Hematologic Parameters Required Prior to Each Dose

	Dose
Neutrophils	$\geq 1000/\text{mm}^3$
Platelets	$\geq 75/\text{mm}^3$
Hemoglobin	$\geq 8 \text{ g/dL}$

- A delay of a dose due to holiday, weekend, inclement weather, or other unforeseen circumstances will be permitted for a maximum of 7 days and not counted as a protocol deviation.
 - Initiation of a dose may be delayed for a maximum of 14 days (28 days from prior dose) to allow a patient sufficient time for recovery from study treatment related toxicity (for example, a delay of 14 days from the planned Day 1 of the cycle). Note that if the Day 15 dose cannot be administered within 7 days of the planned Day 15 (e.g. 21 days from the prior dose (by Day 22), it should be omitted and the next dose administered 28 days of the prior dose as the start of a new cycle. In addition, if there is a persistent downward trend in the predose neutrophil/platelet counts a treatment delay may be considered.
 - In exceptional circumstances, a longer delay is permitted upon agreement between the investigator and the Lilly CRP/CRS. Dosing delay of study drugs due to non-study drug related AEs may be permissible if deemed clinically necessary by the investigator and following discussion between the investigator and the CRP/CRS. The interval between prexasertib doses must not be less than 14 days. If a dose is delayed (for toxicity or other circumstances), the next dose should be adjusted so that there is a ≥ 14 -day interval. If needed, the cycle length should be extended to accommodate the delay.
 - Dose adjustments and delays on either Day 1 or 15 will be made based on the clinical assessment of hematologic and nonhematologic AEs as shown in [Table JTJN.7](#). In addition, the dose can also be delayed or adjusted at the investigator's discretion as clinically indicated.

Table JTJN.7. Dose Adjustments and Delays

Toxicity	CTCAE Grade	Action	Dose Adjustments and Considerations
Neutropenia	Grade 3 or Grade 4	Delay treatment until \leq Grade 2 ($\geq 1000/\text{mm}^3$)	Recommend prophylactic G-CSF ^a
Thrombocytopenia	Grades 2, 3 or Grade 4	Delay treatment until \leq Grade 1 ($\geq 75/\text{mm}^3$)	Investigator discretion
Anemia	Grade 3 or Grade 4	Consider RBC transfusion or EPO (if consistent with institutional guidelines). Delay treatment until \leq Grade 2 ($\geq 8 \text{ g/dL}$)	Investigator discretion
Febrile neutropenia (without prophylactic G-CSF)	Any Grade	Delay treatment until afebrile and neutrophils \leq Grade 2 ($\geq 1000/\text{mm}^3$)	Investigator discretion Recommend prophylactic G-CSF ^a
Febrile neutropenia (with prophylactic G-CSF)	Any Grade	Delay treatment until afebrile and neutrophils \leq Grade 2 ($\geq 1000/\text{mm}^3$)	Reduce to next lower dose level unless there is documented agreement between investigator and CRP/CRS.
Allergic/hypersensitivity reaction ^b	Grade 1 or Grade 2	Administer treatment per institutional guidelines for allergic/hypersensitivity reactions. Monitor closely for any worsening symptoms. A reduced infusion rate can be used for subsequent infusions.	Investigator discretion
	\geq Grade 3	Stop infusion immediately and disconnect infusion tubing from the patient. Administer treatment per institutional guidelines. Patient must not receive any further treatment with prexasertib.	
Other nonhematologic toxicity ^c	Grade 2	Delay treatment until \leq Grade 1 or baseline ^d	Investigator discretion
	Grade 3 or Grade 4	Delay treatment until \leq Grade 1 or baseline	Reduce to next lower dose level

Abbreviations: CRP = clinical research physician; CRS = clinical research scientist; CTCAE = Common Terminology Criteria for Adverse Events version 4.0; G-CSF = granulocyte colony stimulating factor; RBC = red blood cells

^a Refer to Section 7.7.

^b Please refer to the IB for the most recent guidance on allergic/hypersensitivity reactions

^c Except alopecia, fatigue, or toxicities that can be controlled with adequate treatment such as nausea, vomiting, diarrhea, or asymptomatic electrolyte disturbances.

^d Baseline is considered prior to dosing on Cycle 1 Day 1.

If a patient requires a dose reduction, prexasertib should be reduced as shown in [Table JTJN.8](#). After a dose reduction, re-escalation is acceptable.

Table JTJN.8. Prexasertib Dose Reductions

Reduction	Dose
1 st prexasertib dose reduction	80 mg/m ²
2 nd prexasertib dose reduction	60 mg/m ²
3 rd prexasertib dose reduction	Discontinue from prexasertib

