Adverse Events Collection/ CTCAE Grading			X		CTCAE version 4.0.
Concomitant Medication Notation			X		Includes information on over-the-counter and prescription analgesics
Laboratory/ Diagnostic Tests	Hematology			X	See Appendix 2
	Chemistry			X	See Appendix 2
	Urinalysis			X	See Appendix 2
	CA-125			X	Centrally assessed.
	Pregnancy test		X		Women of childbearing potential must have negative pregnancy test prior to biopsy (to confirm eligibility) and a negative pregnancy test within 24 hours prior to drug exposure. Either a urine or serum test is acceptable.
	ECG			X	Single local ECG.
	Pretreatment biopsy		X		May be performed at any time, but sample should be taken only after study eligibility is confirmed.

Schedule of Inclusion and Baseline Assessments

Study Period		Baseline			
Cycle		Baseline (Screening)			
Visit		0			
Duration		Up to 42 days			
Relative Day C1D1		≤42	≤28	≤14	
Procedure Category	Procedure				Comments
Health Outcome Assessments	Worst Pain NRS		X		One question assessing worst pain will be administered by site personnel and completed by the patient prior to extensive interaction with site staff.
	NFOSI-18		X		NFOSI-18 will be administered by site personnel and completed by the patient prior to extensive interaction with site staff.

Abbreviations: C1D1 = Cycle 1 Day 1; CTCAE = Common Terminology Criteria for Adverse Events; ECG = electrocardiogram; ECOG = Eastern Cooperative Oncology Group; EOI = end of infusion; IV = intravenous; NRS = numeric rating scale; NFOSI-18 = National Comprehensive Cancer Network – Functional Assessment of Cancer Therapy – Ovarian Symptom Index-18; RECIST = Response Evaluation Criteria in Solid Tumors version 1.1 (Eisenhauer et al. 2009).

Table JTJN.2. On-Study Treatment Schedule of Activities

Study Period		Cycle				
Cycle/Visit		1		2-n		
Duration		28 days		28 days		
Relative Day within Dosing Cycle		1	15	1	15	
Procedure Category	Procedure					Notes
Physical Examination	Physical examination	X		X		Includes weight and calculated BSA. May be completed up to 7 days prior to treatment infusion.
	Vital signs	X	X	X	X	Includes blood pressure, pulse, and temperature. Complete before each treatment infusion.
	ECOG performance status	X		X		Complete before treatment infusion on Day 1.
Laboratory/ Diagnostic Tests	Hematology	X	X	X	X	May be drawn up to 3 days before the day of dosing. Additional assessments may be obtained at the discretion of the investigator.

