Grade 4 neutropenia was observed in 69% of patients and 75% of the Grade 3 and 4 neutropenia events resolved to Grade ≤ 2 within 8 days after onset; 2 patients (6%) had febrile neutropenia and 56% received G-CSF. Other toxicities included decreased white blood cell (WBC) count (78%), anemia (66%), and decreased platelet count (34%). Nonhematologic adverse events (AEs) included fatigue, nausea, vomiting, and diarrhea (9% each); all were generally mild (Lee et al. 2016). One patient had Grade 3 diarrhea and vomiting during infusion. Only 1 patient (3%) required a dose reduction (80 mg/m²) (Lee et al. 2016).

Figure JTJN.3.1 presents a plot of best responses for target lesions by patient among patients treated with prexasertib. Of the 25 patients treated in Group 2, 20 were evaluable for tumor response. Seven (35%) evaluable patients achieved partial response (PR) (including 2 whose disease was platinum-sensitive and 5 whose disease was platinum-resistant or -refractory). The median duration of response was 6 months (range: 2-13 months), and 5 (25%) patients achieved stable disease (SD) lasting ≥ 4 months, for a DCR of 60%. Patients were heavily pretreated. Platinum-resistant patients had a median of 4 prior lines of therapy (range: 1-13). Of the 7 patients treated in Group 1, 6 were evaluated for tumor response. None of the evaluable patients in Group 1 achieved CR or PR, but 4 (67%) achieved SD lasting ≥ 4 months, for a DCR of 67%. As with Cohort 2, patients had received numerous prior treatments (median: 7, range: 3-12). These preliminary results suggest that prexasertib could be a novel approach to improve the outcomes of patients with HGSOc (Lee et al. 2016).

Abbreviations: *gBRCAm* = germline *BRCA* mutated; HGSOC = high-grade serous ovarian cancer. White bar = platinum-sensitive disease; black bar = platinum-resistant or -refractory disease.

Figure JTJN.3.1 Best response for target lesions, among patients with platinum-sensitive, -resistant, or -refractory disease treated with prexasertib.

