Previous Treatment	Length of Time Prior to First Dose of Prexasertib
Cytotoxic therapies or targeted agents that are small molecule inhibitors	≥21 days or ≥ 5 half-lives, whichever is shorter
Biologic agents that are large molecules including immunotherapy	≥28 days
Investigational agents	≥28 days. If the agent has a long half-life (e.g. >2 weeks), then 3 months or 5 half-lives (whichever is longer) should have passed
Radiotherapy	
Limited-field radiotherapy with palliative intent	≥14 days
Other radiotherapy	≥28 days
Major surgery, excluding biopsy	≥28 days

- [6] Have at least 1 measurable lesion using standard techniques by Response Evaluation Criteria in Solid Tumors (RECIST) version 1.1 (Eisenhauer et al. 2009).
- [7] Have given written informed consent prior to any study-specific procedures and agree and are able to follow the requirements of the protocol.
- [8] Are of an acceptable age to provide informed consent according to the local regulations and are at least 18 years of age.
- [9] Have adequate organ function, as defined below. These values must be met during the baseline visit (prior to biopsy) as well as predose Cycle 1 Day 1:

System	Laboratory Value
Hematologic	
ANC	≥1.5×10 ⁹ /L
Platelets	≥100×10 ⁹ /L
Hemoglobin	≥9 g/dL
Note: transfusions to increase a patient's hemoglobin level or initiation of erythropoietin or G-CSF therapy to meet enrollment criteria are not allowed in the 14 days preceding the first dose of study drug. If a patient receives transfusions, erythropoietin, or G-CSF therapy ≥14 days prior to the first dose, the hematologic criteria listed above must be met following the 14 day window and prior to the first dose of study therapy.	
Hepatic	
Direct bilirubin	≤1.5×ULN
ALT and AST	≤3×ULN OR ≤5×ULN if the liver has tumor involvement
Renal	
Serum creatinine OR	<1.5×ULN OR
Measured creatinine clearance OR	≥40 mL/min/1.73 m ²
Calculated creatinine clearance	
Albumin	
Albumin	>30 g/L OR 25-30 g/L and the value does not decrease across 2 readings separated by ≥14 days (without an intravenous albumin infusion)

Abbreviations: ALT = alanine aminotransferase; ANC = absolute neutrophil count; AST = aspartate aminotransferase; G-CSF = granulocyte colony stimulating factor; ULN = upper limit of normal.

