9.2. Adverse Events

The investigator should provide adverse event (AE) verbatim terms and then the terms will be mapped by Lilly or its designee to corresponding terminology within the Medical Dictionary for Regulatory Activities (MedDRA) Lower Level term (LLT) dictionary. The investigator will use Common Terminology Criteria for Adverse Events (CTCAE) version 4.0 to assign AE severity grades.

Investigators are responsible for:

- monitoring the safety of patients in this study and for alerting Lilly or its designee to any event that seems unusual, even if this event may be considered an unanticipated benefit to the patient
- the appropriate medical care of patients during the study
- documenting their review of each laboratory safety report
- following (through an appropriate health care option) AEs that are serious or otherwise medically important, considered related to study treatment or the study, or that caused the patient to discontinue prexasertib before completing the study. The patient should be followed until the event resolves, stabilizes with appropriate diagnostic evaluation, or is reasonably explained. Frequency of follow-up evaluation is left to the discretion of the investigator.

Lack of drug effect is not an AE in clinical studies, because the purpose of the clinical study is to establish treatment effect.

After the ICF is signed, study site personnel will record via case report form (CRF)/electronic data entry the occurrence and nature of each patient's preexisting conditions, including clinically significant signs and symptoms of the disease under treatment in the study. In addition, study site personnel will record via CRF/electronic data entry any change in the preexisting conditions and any new conditions as AEs. Investigators should record their assessment of the potential relatedness of each AE to study procedure or study treatment via CRF/electronic data entry.

The investigator will interpret and document whether or not an AE has a reasonable possibility of being related to study treatment or a study procedure, taking into account the disease, concomitant treatments, or pathologies. A "reasonable possibility" means that there is a cause and effect relationship between the study treatment and/or study procedure and the AE.

Adverse event grading of toxicities related to estimated glomerular filtration rate (GFR) should be evaluated based on the Cockcroft-Gault method or measured GFR ([Appendix 6](#)).

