Appendix 2. Clinical Laboratory Tests

Clinical Laboratory Tests

Hematology^{a,c}

Leukocytes (WBC)
 Neutrophils^c
 Lymphocytes
 Monocytes
 Eosinophils
 Basophils
 Erythrocytes (RBC)
 Hemoglobin (HGB)
 Hematocrit (HCT)
 Platelets (PLT)

Urinalysis^c

Blood
 Glucose

 Ketones
 pH
 Protein
 Specific gravity
 Urine leukocyte esterase^c

Clinical Chemistry^{a,b}

Serum Concentrations of:

Alanine aminotransferase (ALT)
 Albumin
 Alkaline phosphatase
 Aspartate aminotransferase (AST)
 Bilirubin, direct
 Bilirubin, total
 Blood urea nitrogen (BUN) or blood urea
 Calcium
 Creatinine
 Glucose (random)
 Potassium
 Protein
 Sodium
 CA-125

Pregnancy Test^{c,d}

Urine pregnancy test
 Serum pregnancy test

Abbreviations: CRF = case report form; RBC = red blood cells; WBC = white blood cells.

^a Treatment and enrollment decisions will be based on local laboratory results.

Note: Neutrophils reported by automated differential hematology instruments include both segmented and band forms. When a manual differential is needed to report the neutrophils, the segmented and band forms should be added together and recorded on the CRF, unless the CRF specifically provides an entry field for bands.

^b Central laboratory. In addition, local labs may be collected at investigator's discretion.

^c Local or investigator-designated laboratory.

^d For female patients of childbearing potential.

^e Urine microscopy may be used in place of the urine leukocyte esterase assessment to test for the presence of WBC

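### The platelet threshold for re-dosing is printed as 75/mm³ in Tables JTJN.6 and JTJN.7, 1,333 times below the entry floor: a unit error beside a correct Grade ≤1 rule

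*Protocol*

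**What the plan says.** Protocol Section 7.4 gives the pre-dose platelet condition twice in words and twice as a number.

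- **Rule in words.** The bullet before Table JTJN.6 begins "Neutropenia and anemia must resolve to Grade" ≤2 and sets a stricter level for thrombocytopenia, Grade ≤1. It sends the reader to Table JTJN.6 for the values.
- **Table JTJN.6**, "Hematologic Parameters Required Prior to Each Dose": neutrophils at least 1000/mm³, platelets at least 75/mm³, hemoglobin at least 8 g/dL. No grades appear in this table.
- **Table JTJN.7**, thrombocytopenia row: for "Grades 2, 3 or Grade 4", treatment is delayed until Grade ≤1, with 75/mm³ in brackets as the equivalent.

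The grading scale is named in Section 9.2: "The investigator will use Common Terminology Criteria for Adverse Events (CTCAE) version 4.0 to assign AE severity grades". Neither document reproduces the scale's platelet cut-offs.

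Inclusion criterion [9] in Section 6.1 sets the entry floors: neutrophils 1.5×10⁹/L, platelets 100×10⁹/L, hemoglobin 9 g/dL. It adds: "These values must be met during the baseline visit (prior to biopsy) as well as predose Cycle 1 Day 1". The first dose is therefore covered by the entry floor, and the printed re-dosing number matters from the second dose onward.

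**The concern.** A patient needs 100×10⁹/L platelets to start treatment, yet the tables, taken at face value, would let her be re-dosed at any count from 0.075×10⁹/L upward. A floor that low would hardly ever hold back a dose, so as a check it does nothing.

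The check matters for this drug. Section 3.2.2.3 describes hematologic toxicity as its most frequent and most severe toxicity, and reports deaths after serious bleeding. In the earlier ovarian study, 34% of 32 patients had a decreased platelet count.

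The number is also one that sites have to use directly. Hematology is scheduled for Days 1 and 15 of every cycle in Table JTJN.2 ("May be drawn up to 3 days before the day of dosing. Additional assessments may be obtained at the discretion of the investigator"), and Appendix 2 states: "Treatment and enrollment decisions will be based on local laboratory results". Each site therefore compares a count in its own laboratory's unit with a printed threshold, so the unit must be right. A reader who goes to Table JTJN.6, as Section 7.4 directs, finds a number with no grade beside it to expose the error.

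**Working it through.** **Step 1: convert the printed number.** One litre is 10⁶ mm³.

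- 75/mm³ × 10⁶ mm³/L = 75×10⁶/L = 0.075×10⁹/L.
- Entry floor: 100×10⁹/L ÷ 10⁶ = 100,000/mm³.
- Ratio: 100,000 ÷ 75 = 1,333. Put the other way, 75 ÷ 100,000 = 0.075% of the entry floor.

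**Step 2: compare with the other two rows.** Entry values come from criterion [9] and re-dosing values from Table JTJN.6, each pair put in one unit.

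| Parameter | Entry | Re-dosing | Entry ÷ re-dosing | Grade required before dosing |
|---|---|---|---|---|
| Neutrophils | 1.5×10⁹/L | 1000/mm³ = 1.0×10⁹/L | 1.5 | ≤2 |
| Hemoglobin | 9 g/dL | 8 g/dL | 1.125 | ≤2 |
| Platelets, as printed | 100×10⁹/L | 75/mm³ = 0.075×10⁹/L | 1,333 | ≤1 |
| Platelets, × 1,000 | 100×10⁹/L | 75,000/mm³ = 75×10⁹/L | 1.33 | ≤1 |

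The neutrophil row uses the same per-mm³ unit and is scaled sensibly. With a factor of 1,000 restored, the platelet row falls in line with the other two.

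**Step 3: compare the number with the grade.** Platelets must recover to a milder grade (≤1) than neutrophils or hemoglobin (≤2), yet the printed platelet floor is by far the smallest fraction of its entry value: 0.075%, against 1.0/1.5 = 67% and 8/9 = 89%. If 75/mm³ were the bottom of Grade 1, then Grades 2, 3 and 4, all of which trigger a delay, would have to lie between zero and 0.075×10⁹/L. The number cannot be a rendering of the rule printed beside it.

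**Step 4: could digits have been lost in reading the PDF?** The same 75/mm³ appears in Table JTJN.6, in Table JTJN.7 and in the copy of the thrombocytopenia row in Appendix 7. In the current tables 1000/mm³ for neutrophils is intact, and criterion [9] retains its ×10⁹/L. A reading loss that hit only the platelet number, three times, is unlikely, though only the source file can exclude it. Amendment (b) edited this row to add Grade 2 and left the number as it was.

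**The case against.** The strongest reply is that the operative rule is already correct. Grade ≤1 stands in the text just before Table JTJN.6 and in the same cell of Table JTJN.7, on a named grading scale. Where a grade and a number conflict, the stricter condition governs. Under Appendix 3 the investigators are oncology specialists, who are unlikely to take 75/mm³ literally. Section 7.4 also lets them delay a dose at their discretion or when counts are trending down. On this view the misprint is conspicuous, editorial and harmless.

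Most of that stands, and it limits the practical risk. It does not remove the defect: a mandatory pre-dose value should not depend on the reader noticing and repairing it, and Table JTJN.6 offers no grade to repair it with.

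Two stronger readings are tempting, and the documents support neither.

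- A reader might infer that the protocol authorizes dosing at 75/mm³, or that it has no valid platelet rule. It has one, in words, in two places.
- A reader might scale the 34% with decreased platelets up to this trial and treat the result as patients at risk of a wrong dose. That percentage carries no grades, and Grade 1 triggers no delay. The check applies to every patient before every dose, so the percentage does not measure how often it is used either. Nothing in the documents shows that any site misread the tables.

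It is also fair to object that the CTCAE cut-offs are not in the documents. That the printed value is wrong follows from internal evidence. The replacement value is an inference.

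**Conclusion.** The point holds as a unit error, most likely a missing factor of 1,000, in a mandatory pre-dose safety check. The printed platelet floor is 1,333 times below the entry floor and does not express the Grade ≤1 rule. The error sits in two cells of the current text, and in Table JTJN.6 the wrong number stands alone. It should be corrected, but practical risk is limited because the rule in words is correct and governs.

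The conclusion rests on the tables having been read faithfully from the PDF, which the repeated occurrence supports. Confidence is high that 75/mm³ is wrong. It is lower for 75×10⁹/L as the intended value, because that comes from the pattern of the other rows and not from a stated cut-off. The number of patients affected, if any, cannot be estimated from the documents.

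Nothing here reaches the statistical results. Sample size, endpoints, interim rules and the response analysis do not use this threshold, and SAP Section 5.13.4 grades laboratory values by CTCAE, not by these tables.

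**What to change.** 1. Confirm the platelet floor of Grade 1 in CTCAE v4.0. The inferred value is 75×10⁹/L, that is, 75,000/mm³.
2. Print the confirmed value in the Platelets row of Table JTJN.6 and in the thrombocytopenia row of Table JTJN.7, in ×10⁹/L to match inclusion criterion [9].
3. Send sites a short clarification that Grade ≤1 governs platelet re-dosing and that the printed 75/mm³ is a unit error.

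The cost is two table cells, one site communication, and submission of the change to the ethics boards with the next amendment. No statistical section of the protocol or SAP needs to change.
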